While the effectiveness of SNM has been well established in non-neurogenic disorders variable success has been achieved in the treatment of chronic NGB⁴⁷⁻⁵². In regards to the treatment of neurogenic overactivity specifically, results from several studies demonstrate improvement^{40,53}. In one study of 39 patients with mixed NGB etiologies, 80% of patients were able to achieve complete continence and 43% no longer required anticholinergic medications⁴⁰. Both bladder capacity and bladder compliance have also been shown to improve with SNM. Chartier-Kastler et al were able to demonstrate a mean increase in bladder capacity of ~206 ml in a population of partial SCI patients who had motor function below their injury. SNM in patients with NGB from multiple sclerosis (MS) has been the most studied indication and group in the literature. SNM has been found to reduce frequency of voids per day, reduce incontinence by 4-10 episodes per day, and increase voided volume by 77-84mL per void in this population^{54,55}. Multiple studies in MS patients also cite significant improvements in quality of life and patient satisfaction of 75-86%⁵⁴⁻⁵⁶. Importantly, treatment failure in patients with progressive neurologic diseases (such as MS) is thought to be due to disease progression rather than device failure, something that is not present in SCI. The current data in the NGB patient population needs to be interpreted with caution however, due to heterogeneous patient populations, small sample sizes, and lack of randomization. Prospective controlled trials are needed. A randomized clinical trial with a goal enrollment of 54 subjects is currently ongoing to further establish the ideal chronic NGB patient population for SNM⁵⁷. An important aspect of the treatment of patients with chronic NGB with SNM is that largely the patient groups have good motor function, which is thought to be a fair proxy for a largely intact spinal cord. For instance, ability to ambulate with good motor function below injury or disease has been an important predictor in some studies for success of the procedure.

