Despite the success of the above studies in selected populations of patients with chronic NGB, once changes in the neurological control of the bladder have occurred following SCI they are mostly irreversible. In chronic NGB, treatments must be directed at the local muscle level in order to control the high bladder pressures, incontinence and other symptoms. Consequently, the majority of research into the effects of spinal cord injury on the urinary bladder has focused on patients with well-established chronic neurogenic bladder physiology.

Interventions during the acute phase of SCI aimed at preventing the development of, or reducing the symptoms of NGB, remain an understudied area of research.

Purpose and Objectives

AIM 1: To determine the effect of sacral neuromodulation on urodynamic parameters following acute spinal cord injury. The following outcomes will be evaluated by urodynamic assessment at one year post-SCI: (1) maximum cystometric capacity, (2) bladder compliance, (3) presence of detrusor overactivity, and (4) volume and pressure for first detrusor contraction.

AIM 2: To assess the impact of sacral neuromodulation on patient-reported quality of life after acute spinal cord injury. Patient-reported QoL will be assessed using the SCI-QOL bladder question bank and bladder/voiding diaries (Appendix B). Mean SCI-QOL score, daily number of catheterizations, average catheterization volume, and episodes of incontinence per day will be compared between groups at one year post-SCI.

AIM 3: To examine the impact of sacral neuromodulation on quantifiable clinical outcomes. Patients will be followed longitudinally during the study period and assessed for the following: (1) need for anti-cholinergic medications and/or onabotulinum toxin A treatment, (2) number of symptomatic UTIs per year, (3) complications attributable to the device, (4) need for revision of device or leads due to lead migration or failure, (5) development of hydronephrosis.

Study Population

Age of Participants: 18+

Sample Size:

At Utah: 20
All Centers: 60

Inclusion Criteria:

Inclusion Criteria
Age > 18 years
Ability to implant device less than 12 weeks post-SCI
Presence of acute SCI at or above T12
ASIA Scale A or B
Expectation to perform CIC personally or have caretaker perform CIC

Exclusion Criteria:

Exclusion Criteria

Inability to perform CIC

Pre-existing SCI

Pre-existing progressive neurological disorder

Autonomic dysreflexia

Prior sacral back surgery

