Once screened for inclusion and exclusion criteria (see above), patients will be approached and asked if they would like to participate in a randomized, non-blinded study within 12 weeks of the acute spinal cord injury event. Participants screened online through the Facebook advertisement will still require to be seen by the the site PI in clinic prior to consent to the study. They will then be given study material and informational video and allowed sufficient time to make an informed decision regarding participation. In the event that the participant is unable to read or sign the consent form because the participant is illiterate, visually impaired, or physically unable to sign, we will use a witness to confirm the consent process and sign/date the consent form. Not only will this help us achieve enrollment goals, but it will ensure patient safety and prevent discrimination.

Procedures:

PI and Research coordinators/Asistants will review charts for study eligibility. Future participants will have a choice to view an information video about the study. Then patients will be consented by a member of the study team.

Pregnant women will be excluded from participation. Women who are at risk of pregnancy will be asked to have a pregnancy test before taking part to exclude the possibility of pregnancy. Women of childbearing potential must use an effective contraceptive during the course of this study. Acceptable methods of birth control include abstinence, oral contraceptives, the contraceptive patch, the contraceptive ring and condoms.

60 patients will be enrolled and randomized (30 per arm) to either standard

neurogenic bladder management or standard management plus implantation of the Medtronic PrimeAdvanced Surescan 97702 Neurostimulator.

All patients will receive usual standard of care bladder management for neurogenic bladder. Specifically, standard treatment entails the following: (1) CIC at regular timed intervals if the patient is physically able to do so, if not able to physically perform self catheterization patients will have the option to have this performed by a caregiver (2) treatment with anticholinergic medicine or onabotulinum toxin A as indicated to increase bladder compliance, decrease urinary leakage, and lower bladder pressures to prevent renal damage, (3), undergo routine follow up in the urology and physical medicine and rehabilitation clinic, (4) upper tract imaging (typically consisting of a renal ultrasound) will be

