performed at one year follow-up to monitor for the development of hydronephrosis, (5) and serum creatinine as an estimate of renal function will be collected annually per recommended screening protocols.⁶²

The PrimeAdvanced Surescan 97702 Neurostimulator is an implantable device marketed by Medtronic (Minneapolis, MN) for use in the United States. It has several components: a internal pulse generator (IPG) which delivers an electrical signal to the sacral nerve; a quadripolar electrical lead that is implanted alongside the S3 nerve root; and a programmer that is used to control the electrical pulse delivered by the IPG. The IPG and the lead are permanent implants. The programmer is a handheld device that is not implanted. The PrimeAdvanced 97702 is an FDA approved device for spinal cord stimulation rather than sacral nerve root stimulation, which is the intention of this study. The PrimeAdvanced 97702 is conceptually and functionally, similar to the InterStim II Model3058 neurostimulator which is FDA approved for sacral neurostimulation in the United States. Unlike the Interstim II, the PrimeAdvanced has the ability to accommodate and simultaneously stimulate bilateral leads. All the preliminary studies in acute spinal cord injury have utilized bilateral sacral stimulation. A standardized surgical procedure will be implemented across all three study centers. Specifically, all patients will receive pre-procedural antibiotics of weightbased dosed Vancomycin and Gentamycin unless allergy precludes use of these antibiotics. In those cases, Clindamycin or other broad-spectrum antibiotics will be used. All antibiotics will be administered within 60 minutes of incision. Depending on patient factors, the procedure will be performed under either local or general anesthesia. All cases will have a surgical prep consisting of betadine scrub and paint over the surgical site followed by chlorhexadine prep application. Surgical transparent drape will be used to cover the surgical field and still allow for visualization of perianal area. Antibiotic irrigation will be used for all steps of the procedure. We will localize the S3 foramen with fluoroscopy and the tined lead will be placed with the curved stylet after demonstration of an optimal motor response (anal bellows). Importantly, tined lead stimulation of the S3 nerve roots activates striated fibers via efferent motor nerves. This pathway remains intact even during spinal shock when the spinal reflex arc is inactive. Therefore, the method to perform lead placement can proceed as in a neurologically intact patient. Tined leads will be placed bilaterally. Both leads will be tunneled to a subcutaneous pocket located in a non-pressure bearing location depending on patient body habitus, generally near the posterior iliac crest or anterior abdomen. Leads will be attached to the Prime Advanced IPG. We will permanently save fluoroscopic images in the lateral and anterior-posterior position to allow for comparison in case of suspected lead migration. Patients will take oral cephalosporin or equivalent for 7 days post-operatively.

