Each patient will be evaluated intraoperatively as is standard clinical practice to select stimulation parameters that result in typical, consistent physiological responses (e.g. anal bellows and first toe rotation). The default 14 Hz frequency will be maintained. The electrode with the lowest amplitude stimulation as a proxy for the most closely placed electrode to the S3 nerve. This electrode be trialed first. The stimulation amplitude will be set at 0.7V per protocol as was utilized in the one prior bilateral SNM study in acute SCI. Note: If the subject has S3 sensation (incomplete SCI), the amplitude will be set 0.1V lower than the level of sensation. In such sensate patients, each lead will be programmed individually and then both leads will be activated simultaneously to determine whether further amplitude reduction is needed. These parameters will be set during the initial programming session and will remain constant for the duration of the study. All study centers will utilize the same protocol.

Standardized demographic data based on the National Institutes of Neurological Disorders and Stroke (NINDS) Common Data Elements (CDEs) will be collected via patient interview and evaluation of the electronic medical record including mechanism of SCI and medical comorbidities. All measured outcomes are listed in Table 1 by Aim. At enrollment, all participants will complete the following: (1) standardized 3-day voiding diary to annotate the catheterization time, amount and time of fluid intake, and incontinence events, (2) 24 hour pad weight test, (3) 3-day bowel diary to quantify baseline bowel habits; (4) inventory of current medications; and (5) the SCI-QOL questionnaires (Appendix B). (6) 24 hour pad weight test averaged over 3 days. Repeat measurements will be obtained during clinic visits at 3, 6, 9, and 12 months after enrollment. (7) All participants will undergo baseline urodynamic testing at enrollment. For patients randomized to the intervention arm, urodynamic testing will be completed less than 2 weeks before implantation of the device. Urodynamic testing will be repeated at 3 months and then again at 12 months.

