At each time point, a retrospective review since the prior time point will be performed in order to capture major events such as hospitalizations, additional surgery or death as well as additional subjective data. Those additional subjective data will include: (1) current usage of anti-cholinergic medications and/or onabotulinum toxin A treatment (2) number of culture proven symptomatic UTIs per year (3) complications attributable to the device, (4) need for revision of device or leads.

A renal ultrasound will be obtained at the end of 12 months to evaluate for the development of hydronephrosis. This will be compared with baseline CT or US imaging obtained during their initial trauma evaluation.

There will be a video available for participants to view for additional information.

Procedures performed for research purposes only:
Implantation of sacral neuromodulator and leads

Statistical Methods, Data Analysis and Interpretation

Sample size calculations for this study were based on a mean maximum cystometric capacity of 220.7 mL (SD=103.3), as reported by Sievert et al 60, and a feasibility of enrolling 30 patients per arm within the study period. After accounting for a 15% loss to follow-up we expect 25 evaluable patients per arm. To achieve 80% power at a 5% significance level with 25 patients per arm (N=50), we can detect an effect size of a 38% treatment effect (84 mL increase in capacity). This calculation was simulated for a two-tailed t-test incorporating one interim and one final look at the data using the O'Brien and Fleming (OBF) method and running 50000 simulations (using PASS v. 11.0.8 software). An interim analysis will be conducted at 50% enrollment (N=26 after loss to followup, 13 patients per arm) accrual, and the decision to stop early will be governed by an OBF significance level of 0.003. A 0.051 significance level will be used to evaluate the final analysis. The DSMB's decision to stop early will be guided both by interim results and clinical judgment, especially in the context of emerging, relevant literature.

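### The plan names neither an allocation method nor an adjusted primary analysis, though the trial spans three centres and two ASIA grades; a model with centre and grade is a near-free gain in precision

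*Combined protocol and SAP*

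**What the plan says.** All references are to the combined protocol and SAP.

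- **Allocation** (Study Procedures, Procedures): "60 patients will be enrolled and randomized (30 per arm) to either standard" management or standard management plus the implant. No sequence method, blocking, stratification or concealment is described anywhere.
- **Centres** (same section, on surgery): "A standardized surgical procedure will be implemented across all three study centers". Study Population gives 20 patients at one centre and 60 overall. It does not say how the other 40 divide.
- **Grade** (Inclusion Criteria): "ASIA Scale A or B". The expected mix is not given.
- **Test** (Statistical Methods, Data Analysis and Interpretation): "This calculation was simulated for a two-tailed t-test incorporating one interim and one final look at the data". The inputs are a "mean maximum cystometric capacity of 220.7 mL (SD=103.3"), an 84 mL difference, 25 evaluable patients per arm, 80% power and 5% significance. No analysis model, covariate, centre term or baseline adjustment appears there or elsewhere.
- **Baseline** (Procedures): every participant has urodynamic testing at enrolment.
- **Programming** (Procedures): the amplitude is 0.7 V by default, but "If the subject has S3 sensation (incomplete SCI), the amplitude will be set 0.1V lower than the level of sensation".

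**The concern.** Two features recorded at entry, centre and ASIA grade, could plausibly relate to bladder capacity, and the plan uses neither in allocation or in analysis. In a trial of 60 patients, an allocation that is not stratified can leave a centre or a grade noticeably uneven between arms. A plain t-test does nothing about a particular imbalance once it has occurred, and it leaves any variation due to centre or grade in the error term.

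At stake are the precision of the estimate and how easily a result can be defended if the baseline table shows an uneven split. Type I error is not at stake.

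**Working it through.** **1. The plan's own power.** Inputs from the sample-size text: difference 84 mL, SD 103.3, n = 25 per arm, two-sided 5%.

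- Standard error = 103.3 × √(2/25) = 29.2 mL.
- Noncentrality = 84 / 29.2 = 2.875, with 48 degrees of freedom.
- Noncentral-t power = **80.4%**. A simulation of the two looks at the stated levels (0.003, then 0.051) gives 80.7%. The stated 80% reproduces.

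**2. Chance imbalance if allocation is unstratified.** This is an assumption, because the plan does not state the method. The calculation covers all 60 randomized patients, split 30:30.

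- *Centre.* The number from a 20-patient centre in one arm is hypergeometric (60, 20, 30). A given centre splits 13:7 or worse with probability 17.0%, and 14:6 or worse with 5.4%. With three centres of 20 (assumed), the chance that at least one does so is **35%** and 13% respectively (simulation).
- *Grade.* A 20-point difference means at least 6 more grade B patients in one arm than in the other (6/30). The share of grade B is assumed:

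| ASIA B among 60 | Probability of a difference of 20 points or more |
|---|---|
| 12 (20%) | 10.4% |
| 18 (30%) | **15.8%** |
| 24 (40%) | 18.7% |
| 30 (50%) | 19.6% |

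**3. What such an imbalance is worth in mL.** Suppose grade alone explains a share R² of capacity variance and 30% of patients are grade B. The gap between grades is then g = 103.3 × √(R² / (0.3 × 0.7)), and a 20-point imbalance moves the contrast by 0.2 × g.

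| R² (assumed) | g (mL) | Shift (mL) | Share of 84 mL | Share of the 29.2 mL standard error |
|---|---|---|---|---|
| 0.05 | 50 | 10 | 12% | 0.35 |
| 0.10 | 71 | 14 | 17% | 0.49 |
| 0.15 | 87 | 17 | 21% | 0.60 |

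**4. Power with centre and grade in the model.** Residual SD = 103.3 × √(1 − R²). Degrees of freedom = 48 − 3 = 45 (two for centre, one for grade). R² now refers to both factors together and is again assumed. This is a single-look calculation at 5% that treats the factors as about balanced between arms.

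| R² | Residual SD (mL) | Power |
|---|---|---|
| 0 | 103.3 | 80.3% |
| 0.05 | 100.7 | 82.3% |
| 0.10 | 98.0 | 84.3% |
| 0.15 | 95.2 | 86.2% |

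If the terms explain nothing, the loss is 80.4 − 80.3 = 0.1 percentage point.

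**The case against.** The best case against the point is that it criticises silence. The plan does not say that allocation is unstratified, and it names the t-test only for sizing. That is right: the supportable statement is that the allocation method and the primary model are not given. The imbalance figures are conditional on an assumed method. Silence does not, however, supply either item.

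Second, random allocation protects the unadjusted t-test: averaged over allocations, chance imbalance is already reflected in the p-value. This also stands. A reader might infer that the planned test is biased or that the trial is underpowered. The documents support neither.

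Third, the gain depends on an R² for which the documents give no figure. That stands too. The case for adjusting rests on the small loss if R² is zero, not on a known gain.

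Two stronger readings are tempting:

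- *That the protocol itself shows grades A and B to differ in response.* The background says "ability to ambulate with good motor function below injury or disease has been an important predictor in some studies for success of the procedure", and describes "good motor function, which is thought to be a fair proxy for a largely intact spinal cord". Both remarks concern ambulation and motor function in chronic neurogenic bladder. They are not evidence about A versus B after acute injury.
- *That the amplitude rule makes grade a prognostic factor to be adjusted for.* The rule turns on S3 sensation and applies only to implanted patients. It points to possible effect modification in the implant arm, which a main effect for grade does not address.

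Finally, small fixed blocks within six centre-by-grade strata would average 10 patients per stratum. The consent section describes the study as non-blinded, so the next assignment could be guessed. That is a sound objection to this form of stratification.

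**Conclusion.** The point holds as a matter of precision and chance imbalance. The plan gives an allocation ratio without a method, and its only named test is an unadjusted one used for sizing. Its 80% power claim is correct on its own inputs.

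The exposure is moderate. An uneven centre is fairly likely and an uneven grade less so. A 20-point grade imbalance would move the estimate by about 10 to 17 mL under the assumptions of step 3, which is well below one standard error. Adjustment adds roughly 2 to 6 points of power at an R² of 0.05 to 0.15, and costs almost nothing at zero.

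Four inputs are assumptions that the documents do not supply: unstratified allocation, equal centres, the grade mix and R². The recommendation to adjust is a cheap improvement and does not depend on any one of them being right.

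**What to change.** Add a short analysis statement: the primary comparison of maximum cystometric capacity at one year is a linear model with treatment, centre and ASIA grade as fixed effects, and the same model is used at the interim look. Baseline capacity can be added, since it is already measured at enrolment. State the allocation method as well.

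The cost is 3 degrees of freedom, or 4 with baseline capacity. Sample size and data collection do not change. If enrolment has begun, the allocation can stay as it is; only the model needs to be specified, before outcome data by arm are examined.

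Stratifying the allocation is optional. If enrolment has not begun, stratify by centre with concealed, varying block sizes, not by small fixed blocks in six strata. Any factor used to stratify should be in the model. Stratifying on a factor and then using a plain t-test is conservative: in a simulation with one balanced two-level factor at an R² of 0.10, the type I error fell to about 3.9%.

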
NOTE: Implantation is usually accomplished via a two-step process involving a placement of the permanent quadripolar electrode alongside the S3 nerve root under local or general anesthesia. This permanent lead is controlled by a temporary external programming device for 7-14 days. If greater than 50% improvement in clinical symptoms over that test period, the IPG is implanted subcutaneously under during a second surgical procedure. Because the study hypothesis dictates early stimulation of the sacral nerve roots with a primary outcome evaluated one year post implant, the quadripolar electrical lead and IPG will be placed in the same procedure. This will avoid delay in stimulation of the sacral nerves during the critical window for preventing adverse neuroplastic changes. Patients will be mostly insensate due to their SCI or being under general anesthesia for the procedure. Therefore, to confirm intraoperative placement we will rely upon expected motor responses (anal bellows and toe flexion). If correct motor responses cannot be elicited intraoperatively than the patients will not undergo implantation and will be included in the randomized arm

but in an ‘intention-to-treat’ manner.

FDA approved programming parameters for the Interstim II system will be utilized in this study as follows. The device will provide continuous stimulation (i.e. always on) without discrete treatment periods. The PrimeAdvanced Surescan IPG is capable of generating a maximum voltage of 10.5 volts, 2 volts higher than the Interstim II system, however, it will be programmed to function within the normal Interstim II system parameters (maximum 8.5 volts). Additionally, it will be programmed to use the same stimulation pulsewidth (210 msec) and frequency (14Hz) as the Interstim II system. The area under the stimulation curve will be the same or less than intended by the Interstim II parameters.

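### Does the printed pulse width, which cannot fit the printed stimulation frequency, call for a change to the plan?

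*Combined protocol and SAP*

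**What the plan says.** The programming settings are in the Procedures part of Study Procedures (combined protocol and SAP). The paragraph opens by tying them to an existing device: "FDA approved programming parameters for the Interstim II system will be utilized in this study as follows". It describes the mode of delivery ("The device will provide continuous stimulation (i.e. always on) without discrete treatment periods"), caps the voltage at the reference system's maximum of 8.5 volts, and says of the remaining two settings that "it will be programmed to use the same stimulation pulsewidth (210 msec) and frequency (14Hz) as the Interstim II system".

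The next paragraph, on programming during the operation, repeats the frequency: "The default 14 Hz frequency will be maintained". It then fixes the settings over time: "These parameters will be set during the initial programming session and will remain constant for the duration of the study". It also says that every center follows one protocol. The pulse width is not given anywhere else, in this unit or any other.

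**The concern.** A pulse repeated at a given frequency must be shorter than one cycle, and the printed pulse is almost three times as long as the cycle. Either one of the two numbers or the unit is therefore wrong as printed.

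These settings are part of the written definition of the experimental treatment. They apply to the 30 patients assigned to the device arm, are meant to be identical at three centers, and are held fixed for the whole study. The implanted device is approved for spinal cord stimulation rather than sacral nerve root stimulation, and the protocol relies on the reference system's parameters for its use here. If centers had to guess a setting, the treatment might differ between them. A group trying to replicate the trial could not obtain the setting from the printed numbers alone.

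**Working it through.** **Inputs** (all from the Procedures part of Study Procedures): pulse width 210 msec, printed once; frequency 14 Hz, printed twice; continuous stimulation with no off-periods. The protocol states these as set values and derives nothing from them, so there is no calculation of its own to reproduce.

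**Step 1. Cycle length.** Cycle = 1000 / frequency = 1000 / 14 = 71.4 msec.

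**Step 2. Pulse as a share of the cycle.** 210 × 14 / 1000 = 2.94, or 294%. Separate pulses need a value below 100%.

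**Step 3. The same limit seen from the other side.** A 210 msec pulse could recur at most 1000 / 210 = 4.76 times per second.

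**Step 4. Can another reading rescue the pair?**

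| Reading | Calculation | Pulse ÷ cycle |
|---|---|---|
| As printed, 14 Hz | 210 × 14 / 1000 | 2.94 |
| Frequency rounded up from 13.5 Hz | 210 × 13.5 / 1000 | 2.84 |
| Frequency rounded down from 14.5 Hz | 210 × 14.5 / 1000 | 3.05 |
| Two leads alternating at 7 Hz each | 210 × 7 / 1000 | 1.47 |

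None falls below 1. The alternating-lead reading also does not fit the text, which chooses this device because it can stimulate both leads at once. Continuous delivery rules out on/off cycling as an explanation. The contradiction stands as printed.

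**Step 5. What depends on these two numbers?** The Statistical Methods section builds the sample size on a mean capacity of 220.7 mL (SD 103.3), 30 enrolled and 25 evaluable per arm after 15% loss, 80% power, and a detectable increase of 84 mL (84 / 220.7 = 38%). The interim look uses a significance level of 0.003 and the final analysis 0.051. Pulse width and frequency enter none of these. They also play no part in the urodynamic, quality-of-life or clinical outcomes listed under Purpose and Objectives.

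**Step 6. Could the printed pair be carried out as it stands?** By Steps 2 and 3 it could not. Whoever programs the device must consult the parameters of the reference system named in the same sentence, and those parameters are the same for every center.

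**The case for a change.** The strongest case for a change is that a protocol should not print a treatment setting that cannot exist. The device is used outside its approved indication, the settings are fixed for the whole study, and three centers are to apply them identically. A reader should not have to leave the protocol to find a value that it claims to state, and the correction would be one line.

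Much of this stands. The arithmetic is exact, no other sentence in the protocol repairs it, and a clean specification would be better. Two things limit its force.

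- **The source of the slip is unknown.** The whole discrepancy could come from the unit attached to a single number. Conversion from PDF can alter a unit symbol, and a typing slip by the sponsor is equally possible. The text cannot distinguish the two. The frequency is printed twice and the pulse width once, but that does not settle which is wrong.
- **The setting does not rest on the printed number alone.** The protocol defines it as equal to that of the named reference system and puts the figure in parentheses. The argument that centers might diverge would need a misreading that could actually be programmed, and this one could not be.

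**Conclusion.** The concern is right about the print and does not lead to a change in the plan. As printed, the pulse would take up 294% of a 71.4 msec cycle, so the two settings conflict. The effect on sample size, significance levels, power, endpoints and analysis is nil, and no effect on how patients are treated has been shown.

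This is a clerical matter. The unit should be checked in the sponsor's source file. If it reads the same there, the pulse width, its unit and the frequency, in both paragraphs where settings appear, must be reconciled with the reference parameters that the protocol cites. That is proofreading, and it alters nothing that the trial does or concludes.

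The conclusion rests on two assumptions: that centers program from the reference system's parameters, as the protocol says, and that the discrepancy is a slip in print rather than an intended setting. The first is supported by the opening sentence of the programming paragraph. The second is supported by the fact that the printed pair cannot be delivered. Which figure or unit is wrong cannot be decided from the documents, and no setting is suggested here.
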